DFN-15 effects on migraine with allodynia
February 27th, 2018

DFN-15 effects on migraine with allodynia

Objectives:

1. To determine whether oral administration of DFN-15 (solution of a COX2 inhibitor celecoxib) terminates migraine attacks when given to allodynic patients 3 hours after attack onset.
2. To determine whether mechanical and heat allodynia that develop during acute migraine attacks could be reversed by late (> 3hrs after attack onset) treatment with DFN-15.

Background:

The majority of migraineurs seeking secondary or tertiary medical care develop cutaneous allodynia during the course of migraine ([name] et al., 2000), a sensory abnormality mediated by sensitization of central trigeminovascular neurons in the spinal trigeminal nucleus ([name] et al., 1998). Triptan therapy can render allodynic migraineurs pain-free within a narrow window of time (20-120 min) that opens with the onset of pain and closes with the establishment of central sensitization ([name] et al., 2004). This calls for the development of drugs that can tackle ongoing central sensitization and render allodynic migraineurs pain-free *after* the window for triptan therapy has expired.

Rational for testing a DFN-15:

Several years ago, we (the [name] group) published a series of papers showing that parenteral administration of ketorolac and indomethacin reverse central sensitization in animals and cutaneous allodynia in episodic migraine patients, and proposed that these actions of the drugs are critical in terminating migraine attacks that are unrelieved by triptan therapy (Jakubowski et al., 2005). The premise behind these studies was that there is an association between headache and inflammation. This association is based on (1) demonstrated efficacy of NSAIDs in treating migraine (Snow et al., 2002), (2) RCT trials showing that the efficacy of oral NSAIDs and oral triptans is equal in treating migraine (Tfelt-Hansen, 2008), (3) epidemiological studies demonstrating the protective role of NSAIDs therapy in preventing patients' transition from episodic to chronic migraine (Bigal et al., 2008; Scher et al., 2010), and (4) the American Academy of Family Physicians, American College of Physicians, and American Society of Internal Medicine guideline recommendation to use NSAIDs as a first-line treatment choice for all migraine attacks (Schroeder, 2003).

Rational for testing DFN-15? In the concluding remarks of our papers on parenteral COX1/COX2 inhibitors we wrote: "Parenteral administration of COX-1/COX-2 inhibitors is impractical in routine migraine therapy as it required that patient travel to

hospitals.” We then concluded the following: “To allow patients to treat themselves at home, it will be useful to develop oral formulations of COX-1/COX-2 inhibitors with comparable bioavailability to the spinal cord.” DFN-15 is a COX-2 selective NSAID. It is extensively expressed in cells involved in inflammation and is upregulated by bacterial lipopolysaccharides, cytokines, growth factors, and tumor promoters. As such, it is used to treat a variety of conditions associated with pain and inflammation.

Study design:

Overall strategy: This study will be a proof-of-concept study to determine the mechanism of action of DFN-15 on cutaneous allodynia and central sensitization. To achieve our objectives, we will determine the cutaneous pain thresholds (mechanical, heat) and headache severity of episodic migraine patients under 3 different conditions: (a) while pain-free, (b) during migraine predosing, (c) 2 hours after treatment with either DFN-15 or a matching placebo.

Participant selection:

COX-2 inhibitors have been shown to have a lower GI toxicity than other more commonly-used NSAIDS. Although, COX-2 inhibitors can have severe cardiovascular and renal adverse events including, but not limited to: myocardial infarction, stroke, heart failure, and hypertension (Mathew et al., 2011). Therefore, the inclusion/exclusion criteria for this study will be designed to minimize adverse events.

Individuals with episodic migraine will be considered for participation in this study. Primary inclusion criteria will be (1) age 18-64 years old, (2) history of migraine with or without aura, based on the International Classification of Headache Disorders (3rd edition) for at least 3 years, (3) two or more migraine attacks per month on average during the previous year, and (4) ability to communicate in English (in order to understand and follow instructions of testing). Exclusion criteria will include: (1) fifteen or more headache days per month; (2) aspirin or NSAID-induced asthma or allergy; (3) pregnancy and/or lactating; (4) history of coronary artery bypass surgery, heart attack, angina, stroke, serious gastrointestinal bleeding, peptic ulcer disease; or chronic kidney disease; (5) having medical conditions requiring use of diuretics or daily anticoagulants; (6) having severe uncontrolled medical problems or medications that may influence measurements or impair ability to participate in the testing (e.g. daily or frequent use of opiates or barbiturates (>8 days per month), or NSAIDs or other analgesics (>14 days per month); known creatinine > 2.5 mg/dl or GFR < 30, severe peripheral neuropathy, dementia, etc.); and (7) having been advised by a health professional not to use COX-2 inhibitors.

Potential participants will be recruited from the Hartford Healthcare Headache Program.

Randomized controlled trial: After screening, which will be performed on a non-migraine day, participants will be randomized in a double-blinded fashion to receive either the active drug (DFN-15) or placebo in a ratio of 4:1. They will be instructed to return to the

clinic during a migraine. At the ‘during-migraine’ visit, which will begin 3 hours after onset of headache, we will document headache intensity, associated symptoms, and mechanical and heat pain threshold (first) before treatment (at 180 min after onset of headache) and (second) at a 120 min after treatment (5 hours after headache onset). Based on our prior experience studying migraine patients, we plan to screen 100 patients to achieve 50 participants completing the 2 study visits as planned. 80/100 patients will be randomized to receive the active drug and 20/100 patients will receive the placebo. The study will be terminated as soon as the first 40 patients who received the DFN-15 and first 10 patients who received placebo completed visit 2.

Screening visit - In the first appointment we will identify patients who are good candidate to participate in the study and measure their pain thresholds following an initial evaluation. This appointment will allow us to train patients in how the quantitative sensory testing is performed.

‘During-migraine’ visit – In the second appointment patients’ headache intensity, associated symptoms, and mechanical and heat pain thresholds will be tested 180 min after the onset of a migraine headache. Pain threshold will be determined within the referred pain area in the head. These tests will provide the pre-treatment data to be compared later with post-treatment data. Once pain thresholds are established, patients will be treated and their headache intensity, associated symptoms and pain thresholds will be re-examined 120 minutes later.

Quantitative Sensory testing (QST): Testing will be done in a quiet room away from noise and distraction. Patients will be able to choose their most comfortable position (sitting on a chair or lying in bed) during the sensory testing. In each testing session, pain thresholds to hot and mechanical stimulation will be determined in the skin over the site to where the pain is referred to. This site includes most commonly the periorbital and temporal regions. Heat skin stimuli will be delivered through a 30x30 mm² thermode (Q-Sense 2016, Medoc) attached to the skin at a constant pressure and their pain thresholds will be determined by using the *Method of Limit*. To determine pain thresholds, the skin will be allowed to adapt to a temperature of 32°C (89.5 °F) for 5 minutes and then warmed up at a slow rate (1 °C/sec) until pain sensation is perceived, at which moment the subject stops the stimulus by pressing a button on a patient response unit. Heat stimuli will be repeated three times each (with 10 seconds between each test) and the mean of recorded temperatures will be considered threshold. Pain threshold to mechanical stimuli will be determined by using a set of 20 calibrated von Frey hairs (VFH, Stoelting). Each VFH monofilament is assigned a scalar number in an ascending order (1 = 0.0045g, 2 = 0.023g, 3 = 0.027g, 4 = 0.07g, 5 = 0.16g, 6 = 0.4g, 7 = 0.7g, 8 = 1.2g, 9 = 1.5g, 10 = 2.0g, 11 = 3.6g, 12 = 5.4g, 13 = 8.5g, 14 = 11.7g, 15 = 15.1g, 16 = 28.8g, 17 = 75g, 18 = 125g, 19 = 281g). Because a linear relationship exists between the log force and the ranked number, mechanical pain thresholds are expressed as VFH numbers (#) rather than their forces (g). Each monofilament will be applied to the skin 3 times (for 2 sec and 2 sec in between each application) and the smallest VFH number capable of inducing pain at two out of three trials will be considered threshold. Skin sensitivity will also be determined by recording patient’s perception of soft skin brushing,

which is a dynamic mechanical stimulus, as distinguished from the VFH, which is a static mechanical stimulus. The equipment used for quantitative sensory testing has an FDA approval. It is routinely used by neurologists, nurses, and pain specialists throughout the country. It imposes no risk or discomfort, and since it is controlled by the patient, stimuli can be stopped at any time. Each QST will last about 10 minutes.

Patient Safety:

Throughout the treatment and testing the patients will be monitored (vitals, etc.) to ensure their safety. If a member of the control group is in excruciating pain and their migraine is intolerable they will be prescribed a rescue medication. In this case the participant will drop out of the study. The participants will have the option to drop out at any point in the study. At the end of the testing (5 hours after migraine onset), if a participant (from either group) is still symptomatic and in pain, they will have the opportunity to have a rescue medication prescribed by one of the specialists at the Headache Center. In the case that a patient does not respond well to the study treatment they will be monitored for at least 1 hour before leaving the clinic.

Data analysis:

Primary endpoint: There are 2 primary endpoints in this study. The first is reduction in headache intensity after DFN-15 treatment, and the second is reduction in skin sensitivity at 2 hours after DFN-15 treatment.

For reduction in headache intensity, level of pain will be documented at 1 and 2 hours after treatment using a visual analogue scale of 0 (no pain) to 10 (worst pain). Comparisons of these ordinal (repeated) measures will be performed using Friedman two-way analysis of variance followed by Wilcoxon matched-pairs signed-ranks test.

For reduction in skin sensitivity (allodynia), pain thresholds will be determined 2 hours after DFN-15 or placebo treatment. Since the detection of pain thresholds depends on subjective data input, several algorithms have been developed in order to minimize subjective variation, and make the results as objective as possible. These algorithms are incorporated into the software program that controls the thermal and mechanical sensory analyzer (Q-Sense 2016). Changes in skin sensitivity will be determined by comparing corresponding pain thresholds obtained in the pain-free session (baseline) to pain thresholds obtained during migraine, first before (untreated migraine) and then after (treated migraine) treatment with DFN-15 or placebo. In healthy subjects, pain thresholds for heat and mechanical skin stimuli range between 42-47 °C (107.3-116 °F) ([Lindblom, 1994](#)), and 75-281 g ([Strigo et al., 2000](#)), respectively. Using a more stringent criteria, we will consider a patient to be allodynic if her/his pain threshold is below 41 °C (105.8 °F) for heat, and below 30 g for skin indentation with the calibrated von Frey hairs. Meeting the criterion for any one of modality will be sufficient to determine that the patient is allodynic at the 'during untreated migraine' testing. For this endpoint, the database will consist of pain threshold measurements in 50 patients, taken while they are pain-free (baseline), during untreated migraine attack (before DFN-15 or placebo treatment), after treatment with DFN-15 or placebo. Only those patients who completed all 3 testing sessions will be included in the data analysis. The resulting distributions will be tested for normality, and their descriptive statistics computed. The differences

between before and after DFN-15 treatment will be computed on a pair-wise basis. To increase the sensitivity of detecting changes, patients in this study will be compared to themselves (baseline vs. during untreated migraine vs. during treated migraine) rather than to control subjects because the large normative range of pain thresholds reduces the sensitivity of detecting allodynia in reference to the normal range. Differences between pain-free vs. during untreated migraine vs. during treated migraine will be computed on a multiple sample pair-wise basis. Differences in mean pain threshold will be judged (significant or not significant) by using appropriate pair-wise multiple sample comparison (Newman-Keuls, Kruskal-Wallis) tests. Alternatively, repeated measurements of pain thresholds (allodynia) will be analyzed using Friedman two-way analysis of variance. Finally, secondary analyses using the collected data may be done as a part of this study including, but not limited to, the duration and intensity of the headache prior to arrival at the clinic.

The primary outcome measure in the current study is the proportion of patients demonstrating a headache intensity decrease that is greater than 50% (post-treatment compared to pre-treatment). Secondary outcome measures are proportions of patients demonstrating allodynia before and after treatment; allodynia to thermal stimuli is defined as a pain threshold < 41 0C, and to mechanical stimuli as pressure pain threshold of < 30 g.

The primary and secondary outcome measures will be examined using the Z test for comparison of independent proportions and Chi-square (χ^2) test to assess the categorical association between the group (treatment / placebo) and (i) reduction rate of headache intensity (below / above 50%; primary outcome measure); (ii) proportion of thermally allodynic participants (pain threshold below / above 41 0C; secondary outcome measure); and (iii) proportion of mechanically allodynic participants (pressure pain threshold below / above 30 g; secondary outcome measure).

Power analysis was based on the Z test for comparison of independent proportions. Incorporated were α of 5% (significance level), 1- β error probability of 90% (power), and allocation ratio of 4:1 (treatment:placebo, respectively). Based on previously published data ([name] et al., Annals of Neurology 2004), the primary outcome measure is expected to be lower in the treatment group; accordingly, power analysis was one-tailed. The primary hypothesis was that post-intervention proportions of patients demonstrating a headache intensity decrease that is greater than 50% in the treatment and placebo groups would be 80% and 30%, respectively. This computation yielded a required number of 9 subjects in the placebo group and 36 patients in the treatment group (critical Z = -1.645). An additional 20% were accounted for potential dropout. Thus, a total of 54 participants (11 placebo, 43 treatment) are to be enrolled in the entire study.

References:

[name] R, Collins B, Jakubowski M. 2004. Defeating migraine pain with triptans: a race against the development of cutaneous allodynia. *Ann Neurol* 55(1):19-26.

[name] R, Yamamura H, Malick A, Strassman AM. 1998. Chemical stimulation of the intracranial dura induces enhanced responses to facial stimulation in brain stem trigeminal neurons. *Journal of Neurophysiology* 79(2):964-982.

[name] R, Yarnitsky D, Goor-Aryeh I, Ransil BJ, Bajwa ZH. 2000. An association between migraine and cutaneous allodynia. *Annals Neurol* 47:614-624.

Schroeder BM. 2003. AAFP/ACP-ASIM release guidelines on the management and prevention of migraines. *American family physician* 67(6):1392, 1395-1397.

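### The protocol gives heart failure as one reason for its eligibility criteria, but no exclusion names it, so a small group with stable heart failure stays eligible as written

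*Combined protocol and SAP*

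**What the plan says.** Under Study design, the Participant selection section first gives the safety background: "COX-2 inhibitors can have severe cardiovascular and renal adverse events including, but not limited to: myocardial infarction, stroke, heart failure, and hypertension". It then draws the consequence: "the inclusion/exclusion criteria for this study will be designed to minimize adverse events".

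The exclusions follow as seven numbered items. The four that bear on cardiovascular and renal risk are:

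- Exclusion (4): "4) history of coronary artery bypass surgery, heart attack, angina, stroke, serious gastrointestinal bleeding, peptic ulcer disease; or chronic kidney disease".
- Exclusion (5): "having medical conditions requiring use of diuretics or daily anticoagulants".
- Exclusion (6): "having severe uncontrolled medical problems or medications that may influence measurements or impair ability to participate in the testing". Its bracketed examples include "known creatinine > 2.5 mg/dl or GFR < 30, severe peripheral neuropathy, dementia, etc".
- Exclusion (7): "having been advised by a health professional not to use COX-2 inhibitors".

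The list opens with wording that does not claim to be complete: "Exclusion criteria will include: (1) fifteen or more headache days per month". The inclusion criteria limit age to 18 to 64 years. Screening takes place on a non-migraine day and precedes randomisation, and the Screening visit paragraph gives it the purpose of finding suitable candidates. Under Patient Safety, vitals are monitored throughout treatment and testing.

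**The concern.** The protocol sets its own test: it names certain harms of the class and says the criteria are there to keep them down. Exclusion (4) applies that logic to two of the named harms by removing people with a past heart attack or a past stroke. It does not do the same for heart failure, which stands in the same sentence.

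What is at stake is the safety of individual participants. A screener working from the written list is not told to turn away a patient with stable heart failure, even though the protocol cites heart failure as a reason for having the list. Validity of the comparison is not in question.

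**Working it through.** No arithmetic applies. The check is to set the stated harms beside the exclusions, and then ask who with heart failure gets through all of them.

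**Step 1. Named harms against named exclusions.**

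| Harm named in Participant selection | Named in an exclusion? | Indirect cover |
|---|---|---|
| Myocardial infarction | Yes, (4) | Not needed |
| Stroke | Yes, (4) | Not needed |
| Heart failure | No | (4) through other listed histories; (5); (6) if severe and uncontrolled; (7) |
| Hypertension | No | (5) if a diuretic is needed; (6) if severe and uncontrolled, on its natural reading; (7) |

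This table counts names. It does not measure risk.

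**Step 2. Heart failure patients who are already removed.**

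- Exclusion (4) takes out anyone with heart failure who also has a past infarction, angina, bypass surgery, stroke or chronic kidney disease.
- Exclusion (5) takes out anyone whose condition calls for a diuretic or a daily anticoagulant.
- Exclusion (6) takes out severe uncontrolled heart failure. Its renal limits have no evident link to sensory testing, so they read as safety limits, and the examples are left open-ended. The broad reading is therefore the natural one.
- Exclusion (7) takes out anyone a health professional has already warned off the class.

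**Step 3. Who is left.** A patient aged 18 to 64 with stable heart failure, none of the histories in (4), no need for a diuretic or daily anticoagulant, and no prior advice against COX-2 inhibitors. Exclusion (6) does not reach this patient on the strength of the heart failure, because on either the narrow or the broad reading its disease limb requires a problem that is both severe and uncontrolled. Its medication limb turns on effects on measurement or ability to take part, and the drugs it gives as examples are opiates, barbiturates, NSAIDs and other analgesics. The remaining exclusions concern headache frequency (1), aspirin or NSAID reactions (2), and pregnancy or lactation (3). None concerns heart failure.

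**Step 4. How many.** The documents give no frequency of heart failure in the recruiting clinic, and none for the narrowed group in Step 3. The number affected cannot be computed.

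**Step 5. Effect on the statistics.** The power analysis under Data analysis uses a one-tailed 5% level, 90% power, 4:1 allocation and response proportions of 80% and 30%, giving 36 + 9 = 45 patients. Adding a term to an exclusion applied before randomisation changes none of these inputs.

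**The case against.** The case for leaving the text alone has several parts.

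*Listing a harm does not promise a matching exclusion.* This is correct. The protocol undertakes to minimise adverse events, and indirect criteria can do that. A reader might infer that the protocol contradicts itself. It does not, and the point is only that one gap is left. Since (4) already treats a history of two named events as a reason to exclude, extending it to a third follows the protocol's own approach.

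*The list is open-ended and screening selects suitable candidates.* This also stands: an investigator may exclude such a patient. But permission to use judgement is weaker than an instruction.

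*The risk of this use is not shown.* This stands too. The source cited for the harms is a mini review of COX-2 inhibitors in arthritis, whereas this trial gives one treatment in clinic. Vitals are monitored, and patients who do not respond well are watched for at least 1 hour. The documents do not say how large the risk of one treatment is in stable heart failure. Monitoring can detect a problem, but it is not an eligibility rule.

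*Hypertension.* A reader might infer an equal gap here, since no criterion names it. The documents do not support that. Exclusion (6), naturally read, already covers severe uncontrolled hypertension, and (5) removes patients whose hypertension calls for a diuretic. Naming uncontrolled hypertension in (6) would be a helpful clarification, but without a blood pressure limit it would still leave the screener to interpret it. It is not part of this point.

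**Conclusion.** The point holds in a narrow form. Heart failure is a stated reason for the eligibility criteria, no exclusion names it, and the patient described in Step 3 of the working is eligible as written. This rests on the text of the seven exclusions, with (6) given its broader reading in the protocol's favour.

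The size is unknown and probably very small. That is a judgement, based on the age limit and on how much of the group (4) to (7) already remove. Any assumed prevalence would have no source in the documents, so no expected count or probability of exposure is offered.

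A reader might infer that heart failure patients in general are admitted, or that participants face a demonstrated danger. The documents support neither: most routes into the trial for such patients appear closed already, and the risk of one treatment is not quantified. There is no effect on sample size, error rate or analysis. This is an optional, cheap improvement.

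**What to change.** Add *heart failure* to the history list in exclusion (4), and apply it at the screening visit, before randomisation.

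The cost is one term in the protocol and, at most, a few otherwise eligible patients turned away at screening. Because they are turned away before allocation, the change causes no loss after randomisation. The migraine visit, the sample size and the analysis stay as they are.

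If the sponsor is editing the list anyway, uncontrolled hypertension could be named among the examples in (6) as a wording clarification, preferably with a stated blood pressure limit.

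### Stopping on arm quotas of completers replaces rescued placebo patients with unrescued ones, which would bias against DFN-15, and leaves surplus patients and recruitment size undefined

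*Combined protocol and SAP*

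**What the plan says.** Under Study design, the Randomized controlled trial paragraph states that "participants will be randomized in a double-blinded fashion to receive either the active drug (DFN-15) or placebo in a ratio of 4:1". This happens after screening and before the migraine visit. The target is given as "we plan to screen 100 patients to achieve 50 participants completing the 2 study visits as planned", followed by "80/100 patients will be randomized to receive the active drug and 20/100 patients will receive the placebo". So the same 100 patients are both screened and randomised. Recruitment ends on two separate counts: "The study will be terminated as soon as the first 40 patients who received the DFN-15 and first 10 patients who received placebo" have completed the second visit.

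Patient Safety adds: "If a member of the control group is in excruciating pain and their migraine is intolerable they will be prescribed a rescue medication". Such a patient leaves the study.

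Data analysis says, for the skin-sensitivity endpoint, that "the database will consist of pain threshold measurements in 50 patients", and limits the analysis to patients with all three testing sessions. No separate analysis set is given for the primary outcome measure, the proportion with more than a 50% fall in headache intensity.

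The power paragraph that closes Data analysis gives different recruitment figures: 9 placebo and 36 DFN-15 patients required, 20% added for dropout, 54 enrolled (11 and 43).

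**The concern.** Three things follow from reading these sections together.

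First, a placebo patient who is dosed and then rescued does not count towards the 10. Recruitment goes on until 10 placebo patients have got through the two hours without rescue. Patients rescued for intolerable pain are very unlikely to be on course for a halving of pain, so their removal leaves a placebo group with too many responders. With only 10 placebo patients, each such replacement matters.

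Second, both quotas must fill. Unless the arms reach 40 and 10 on the same patient, one arm overshoots. The plan does not clearly say whether the extra completers are analysed, and that choice should be fixed before data are seen.

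Third, 80 and 20 randomised at 50% completion give 40 and 10 only on average. The plan does not say what happens if 100 patients fall short, or who counts completers by arm in a double-blind trial.

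**Working it through.** **The plan's own sample size.** Inputs from the power paragraph: "Incorporated were α of 5% (significance level), 1- β error probability of 90% (power), and allocation ratio of 4:1", one-tailed, responder rates 80% and 30%. The pooled rate is (0.30 + 4 × 0.80)/5 = 0.70.

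- Placebo n = [1.645 × √(0.70 × 0.30 × 1.25) + 1.282 × √(0.30 × 0.70 + 0.80 × 0.20/4)]² / 0.50² = (0.843 + 0.641)²/0.25 = 8.8, so 9 placebo and 36 DFN-15.
- Power at 9/36 is 90.6%, and 45 × 1.2 = 54. The stated figures reproduce.

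**Selection of placebo completers.** Take 30% as the rate among all treated placebo patients. Let r be the share of placebo non-responders who are rescued and leave. The documents give no value, so r is an assumption. The rate among completers is 0.30/(0.30 + 0.70 × (1 − r)):

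| r | Placebo rate among completers |
|---|---|
| 10% | 0.30/0.93 = 32.3% |
| 20% | 0.30/0.86 = 34.9% |
| 30% | 0.30/0.79 = 38.0% |
| 40% | 0.30/0.72 = 41.7% |

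At r = 20%, 0.70 × 0.20 = 14% of treated placebo patients disappear, and the planned 50-point difference shrinks to 80 − 34.9 = 45.1 points. For power at 40/10, the pooled rate is (0.349 + 3.2)/5 = 0.710. Then z = [0.451 − 1.645 × √(0.710 × 0.290 × 0.125)] / √(0.349 × 0.651/10 + 0.80 × 0.20/40) = (0.451 − 0.264)/0.163 = 1.15, which is about 87%. The same formula gives 93.0% at 80% against 30%.

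This takes Patient Safety literally, with early rescue mentioned only for the control group. If the same 20% applied to DFN-15 non-responders, that rate would become 0.80/(0.80 + 0.20 × 0.80) = 83.3%, and the difference would be 83.3 − 34.9 = 48.4 points.

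**Passing 50 completers.** The rule stops at exactly 50 only if the 50th completer leaves a 40/10 split.

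- Fixed 80/20 with 50 completers drawn: probability 0.197, so 80% pass 50.
- Simple 4:1 allocation: probability 0.140, so 86% pass 50.
- Permuted blocks of 5 at 50% completion (simulated): about 81% pass 50. At 80% completion this falls to 70%.

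The median number of completers at stopping is 52 to 54, a surplus of 2 to 4. The 90th percentile is 61 to 69.

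**Filling both quotas within 100.** The implied completion rate is 50/100 = 50%. With independent completion at the same rate q in both arms and 80/20 randomised, P = P(Bin(80, q) ≥ 40) × P(Bin(20, q) ≥ 10):

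| q | DFN-15 ≥ 40 | Placebo ≥ 10 | Both |
|---|---|---|---|
| 45% | 0.215 | 0.409 | 0.09 |
| 50% | 0.544 | 0.588 | 0.32 |
| 55% | 0.844 | 0.751 | 0.63 |
| 60% | 0.973 | 0.873 | 0.85 |
| 80% | 1.000 | 0.999 | over 0.99 |

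Simple 4:1 randomisation of 100 gives 0.25 at q = 50%. With blocks of 5, the median number randomised to fill both quotas is 107 and the 90th percentile is 130. Any screen failure among the 100 lowers these probabilities.

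**The two recruitment plans.** One implies 50% completion. The other implies 45/54 = 83%. Enrolling 43 and 11 would meet the 40 and 10 quotas only with completion of 40/43 = 93% and 10/11 = 91%.

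**Stopping at 50 completers overall.** The placebo count would fall below the required 9 in 23% (blocks of 5) to 31% (simple) of trials. Exact power of the pooled Z test is 92.7% at 40/10, 89.6% with 8 placebo and 86.4% with 7.

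**The case against.** The selection of unrescued placebo patients comes from dropping rescued patients and analysing completers, not from the quota itself; it would exist under any completer-based rule. That stands. The quota adds replacement, so the loss never shows as a shortfall in the placebo arm. The bias also works against DFN-15, so it does not threaten a false claim of benefit.

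A quota is a defensible protection for an arm of 10, and 40/10 exceeds the required 36/9. That stands too, and it is why a plain stop at 50 completers is not the remedy.

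Four stronger readings are tempting and are not supported:

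- **The rule breaks the blind.** Someone must know the allocation to apply it, but an independent person could count arms without telling the assessors. Continued recruitment reveals no individual's treatment. This is an unstated procedure, not a breach.
- **The trial fails two times in three.** The 100 is a planning number, not a cap; a shortfall means recruiting more. The 32% also depends on 50% completion.
- **Surplus completers are discarded.** No sentence says so. The count of 50 describes one endpoint's database, and the explicit criterion there, all three sessions completed, would admit every completer.
- **Type I error is inflated by the rule.** It depends on counts, not outcomes, so it does not do this by itself.

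**Conclusion.** The concern holds as a change that should be made, not as a fatal flaw. Read together, the stopping rule, the rescue provision and the completer analysis give a placebo group enriched for patients who did not need rescue. The size depends on a rescue rate that the documents do not give: from 30% to about 35% if one in five placebo non-responders is rescued, with a range of 32% to 42% for rescue of 10% to 40%. This assumes that rescued patients would not have responded and that 30% is the rate among all treated placebo patients.

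The overrun past 50 is likely but usually small. Meeting both quotas within 100 is about a one-in-three event only if completion is 50% and all 100 are randomised 80/20; at 60% or more it is likely. The power calculation reproduces. What is missing is how surplus patients are analysed, who counts by arm, and one consistent recruitment plan.

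**What to change.** 1. Analyse every randomised patient who was treated, with no cap in either arm. On the outcome of more than 50% reduction, count treated patients who leave for rescue before 2 hours as non-responders, by the same rule in both arms.
2. Choose one recruitment rule. Either fix the number randomised, in permuted 4:1 blocks, or keep a placebo minimum and name an independent unblinded person to track arm counts and tell the site only when to stop. Do not stop at 50 completers overall without a placebo minimum.
3. State the number screened separately from the number randomised. Reconcile the 100 patients at about 50% completion with the 54 enrolled at 20% dropout.
4. Reconcile the early-rescue sentence, which refers to the control group only, with the double-blind design.

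The cost is protocol and analysis wording, plus a small independent role if a placebo minimum is kept. The final split may differ from 40:10, and observed responder rates may be slightly lower because rescued patients now count.
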